Males who present with exclusion criteria for one of the medical reasons listed above will be referred to the appropriate specialist for management of their conditions. Additionally, any men who have an anatomic contraindication but still want circumcision, can be referred to an urologist for further management. In keeping with standard national practice, clients presenting with specific disease conditions such as STIs or TB may be treated on-site or referred for care elsewhere if appropriate services are not available on site. Furthermore, males who are HIV+ will be assessed to determine if they are on antiretroviral therapy (ART). Those not on ART will be referred for ART.

Client Withdrawal Criteria

A client has the right to withdraw from the evaluation at any time, for any reason, without prejudice to his future medical care by the provider or the health facility (see Appendices V and VI for the client and minor client assent forms). If a client withdraws after consent, but prior to device placement, the client will be replaced until the desired sample size is reached and the data will be excluded from analysis. If a client withdraws after device placement, the client will not be replaced and the existing data will be included in the analysis, but no attempts will be made to collect further data other than that required for clinical documentation of the removal visit. The reason, timing and circumstances of the withdrawal will be documented and analyzed. The client will subsequently not be included among those selected for the day 28 in-person interview, nor will they be asked to return for the day 49 follow-up visit to assess healing. When the client withdraws, they will be informed that they may still return to the clinic for removal of the device as scheduled, and contact the clinic should they have further questions, suffer an AE, or experience other difficulties healing.

A client will be informed in advance that if he wishes to withdraw from the evaluation after ShangRing placement but before scheduled removal, he must still return to the provider for device removal on day 7 for his own health. The client will also be advised that once applied, it is not safe to remove the device before day 5. If the client requests removal on day 5 or 6, it will be removed as requested. The number and reasons for client withdrawals will be recorded and included in the final evaluation report (See Appendix XXII).

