Procedure for Handling Clients Lost-to-Follow-Up

Clients who are lost to follow-up after device placement, and therefore do not return to have the device removed, will not be recorded as experiencing an AE, and also will not be included in calculations when measuring AEs.

In the event that a client refuses to return for follow-up, ShangRing has been shown to detach on its own. Studies show that for those clients who do not come in to have the device removed, and wear it for more than

seven days, the ShangRing will eventually spontaneously detach on its own, and healing will progress normally. In one study, complete detachment of the device occurred in 66.7% of men who wore the device for more than seven days, and 14% of men requested removal of a partially detached device 8-14 days after placement. No severe or serious AEs were reported among this group.²⁹

A study of delayed removal of ShangRing in Kenya found that in 81.8% of men the ShangRing had completely detached on its own between 10-16 days after circumcision.³⁰ By 21 days following the circumcision the ring had at least partially detached in 100% of men, and was completely detached in 93.7%. While the ShangRing has been found to be safe if left on, this is not the recommended standard of care for the purposes of this evaluation, and clients will be followed up with for device removal as described in this protocol.

Provider Participant Inclusion Criteria

Providers meeting the following criteria will be included in the evaluation:

- Adult aged 18 or older
- Employed as a medical doctor, Assistant Medical Officer, Clinical Officer, professional nurse, or enrolled nurse at the participating sites in Shinyanga, Tanzania
- Experienced in providing conventional surgical circumcision
- Trained and certified in ShangRing circumcision techniques for the current evaluation by a trainer who is trained in ShangRing application, and has performed a minimum of 10 placements and 5 removals. The evaluation team will bring in ShangRing master trainers from countries with prior ShangRing experience (i.e. Kenya, Zambia) to train providers based in Shinyanga who will then train mid-level providers to conduct ShangRing circumcision, or send physicians from Tanzania to these countries for training.
 - Trained and competent in identifying and managing complications related to ShangRing circumcision.
 - Trained and competent in screening clients to determine their eligibility for ShangRing circumcision.

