Follow-Up Visits

Active follow-up will be initiated for clients who fail to return on day 7 post-placement to have the device removed, or for other visits (e.g. AE follow-up) recommended by the ShangRing clinician. Each implementing site will assign staff to conduct follow-up telephone calls and home visits as needed. All active follow-up efforts will be documented on the appropriate forms designed for this purpose (Appendix XI). For clients who fail to return for device removal on day 7, active follow-up will start on day 8. Active follow-up will start with telephone calls to the contact number(s) provided by client and recorded on the locator information sheet at enrolment. An

introductory script for contacting clients by phone is attached as Appendix X. If a client is not reachable through direct voice calls, short text message reminders will be sent to his contact phone number. The reminder text message will include client name and specify the name and phone number of the clinic reaching out to him. The text message will not include the purpose of appointment visit for which the reminder is sent. Up to five calls will be made to reach the client; one per day starting on day 8, and continuing over the next 4 days through Day 12 (5 days post-procedure).

Once contact is made, the staff member will reinforce the importance of device removal and encourage the client to return to the circumcision site. If the client states that he is not able to return by day 9 post-placement, or the schedule day, or does not in fact return by day 9 or the schedule day, the staff member will attempt to verify the addresses provided to schedule an appointment at one of the address locations provided for device removal on day 9, or as soon as possible. If the client has not been successfully contacted by day 9 or the scheduled day, home tracing visits to the address he provided will begin. These will total up to 4 visit attempts on different days if necessary to reach the client.

For clients not under follow-up for AEs who miss scheduled visits other than the day 7 visit, follow-up will be done through phone by text messages or voice calls only, except in exceptional circumstances where a clinician deems physical follow-up necessary.

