Appendix XII – ShangRing Case Report Form: Client Follow-Up Form

CASE REPORT FORM – ShangRing DEVICE FOLLOW-UP

Evaluation of the safety and acceptability of the ShangRing device for male circumcision in Tanzania

Site Code:

Client ID # (CID):

INSTRUCTIONS FOR THE PROPER COMPLETION OF THE CRF

Please follow the instructions below:

1. This form is to be used for ALL follow-up visits, including the removal visit, and unscheduled visits.
2. Complete a new form at each follow-up visit.
3. Use a ball-pen, DO NOT use a pencil, a marker or a fountain pen.
4. Make sure to place the separator provided under the last copy of each page so that data recorded on one page does not copy to the next.
5. Subject initials will be comprised of the first letter of the first name followed by the first two letters of the surname.
6. Fill in the form in a clear, concise and readable way. Use common medical terminology.
7. Correct wrong data by crossing out the information with a single line and writing the correct data next to it. The evaluation coordinator, or the site coordinator in the evaluation coordinator's absence, will initial and date the correction.
 - a. Example: 07/03/1969 corrected to 09/03/1969 (with initials and date of the correction)
8. Complete all the available fields, DO NOT leave empty fields.
 - a. For evaluations not performed record ND (not done).
 - b. For data not relevant to the subject or stage of evaluation record NA (not applicable).
 - c. If you do not know the data, please use the initials UNK (unknown).
 - d. Use leading zeroes if necessary (e.g.: 15 mg = 0 1 5 mg).
 - e. Make sure to complete every header on each page.
9. Please make sure to **circle the correct option** whenever it is requested.
10. Please DO NOT add wording to CRF pages unless required. For any additional comments please use the Comments Sheet at the end of the CRF modules.
11. Dates (e.g., date of birth, date of visit) will be recorded in the DD/MM/YYYY format.
 - a. Example: 19 June 2017 will be recorded as 19/06/2017
12. CID is the Client Identification Number. It comprises the initials of the site followed by the four digit enrollment date and the three digit subject consecutive number. Example: Subject number 1 in Good Hope Health Center enrolled on July 21 will be GH2107001.
13. Time will be recorded in 24:00 format.

Example: 6:15 pm will be recorded as 18:15

ShangRing Client Follow-Up Form

Client ID Number: _____

Date of visit (dd-mm-yyyy): _____

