Date of ShangRing Device Placement (dd-mm-yyyy): _____

Contact Type (select one):

- **On-site visit (specify name of facility/site):** _____
- **Off-site visit (specify location, i.e. work, home, school):** _____
- **Phone contact (number called):** _____

Type of Visit (select one):

- Removal visit (specify days since device placement): _____
- Day 42 post-placement healing assessment (specify day if client comes in on different day): _____
- Post day 42 follow-up healing assessment (specify days since device placement): _____
- Unscheduled visit (specify days since device placement): _____

Is there a photographer present to take pictures of the procedure (circle one): Yes No

(If 'No,' do not proceed until a photographer is available. Photos must be taken with the photo frame, including client ID number, date and pain score before and after device removal).

Has there been a change to the client's medication since device placement (circle one): Yes No

(If 'Yes,' please record the medication on the medications CRF page).

Summary of Follow-Up:

Clinical course leading to client's visit today: _____

Care/advice provided:

Medication given (circle one)? Yes No

If yes, drug (name, dose and total quantity dispensed):

For removal visit, was anesthesia required during removal (circle one): Yes No NA (not removal visit)

If "Yes," what? _____

For removal visit, were there any device-related events or AEs that occurred during the removal (circle one):

Yes No NA (Device not removed this visit)

If "Yes," please record on Adverse Events form.

For removal visit, provider evaluation from 1 to 10 (1 being worst): _____

Name of provider who removed the ShangRing device: _____

Healing status observed by clinician (select one): Healed Not Healed NA (pre-day 42 visit)

Clinical healing defined as: clinical healing after MC by any method is intact epithelium (unbroken skin) covering the wound as judged by the provider on visual inspection, meaning that none of the following are present: sutures, scabbing, drainage, moisture, gaps between epithelial edges or ulceration.

Was client instructed not to masturbate until completely healed (select one)? Yes No NA (client healed)

Was client reminded to abstain from sexual intercourse until completely healed (select one)?

Yes No NA (client healed)

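### The follow-up form tells staff not to proceed without a photographer, so as written device removal can be held for an optional evaluation photograph

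*Protocol*

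**What the plan says.** The follow-up form in Protocol Appendix XII is completed at every follow-up visit, including removal and unscheduled visits, and its contact types include off-site visits. One item asks whether a photographer is present, with Yes and No as the only answers. If No, staff are told "do not proceed until a photographer is available". The same parenthesis continues: "Photos must be taken with the photo frame, including client ID number, date and pain score before and after device removal".

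Elsewhere the protocol says the following.

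- **Timing of removal.** Under Client Withdrawal Criteria, a client who withdraws while wearing the device is told that "he must still return to the provider for device removal on day 7 for his own health". For earlier requests, "If the client requests removal on day 5 or 6, it will be removed as requested". Under Follow-Up Visits, for a client who cannot or does not come back by day 9, staff try to "schedule an appointment at one of the address locations provided for device removal on day 9, or as soon as possible".
- **Photographs are optional.** The Photography section requires consent before each photograph, lets clients refuse at any point and keeps refusers in the evaluation. The screening form (Appendix VII) also says that declining does not exclude a client.
- **Use of the photographs.** They help investigators verify adverse events (Photography) and supplement the endpoint analysis (Analysis Overview).

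**The concern.** Staff work from this form at the visit. Followed literally, it makes removal of a device that is due, or overdue, depend on someone being there to take pictures. No timing rule elsewhere in the protocol carries that condition, and the photographs are supplementary material that the client may decline. At stake is an avoidable delay to a clinical step, most plausibly for clients who have already missed their removal date and are being seen at home or work. The form also omits the right to decline, so it gives staff no prompt or response option for a foreseeable situation.

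**Working it through.** No calculation applies. The check sets the form against the rest of the protocol.

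1. **What triggers the stop.** The condition is a No to the photographer question, so the trigger is the photographer's absence. The words that follow name no exception for an urgent visit, a withdrawn client or an off-site removal.
2. **Whether it reaches removal.** The item carries no removal-visit label, but it concerns pictures of the procedure, and the next sentence refers to photographs before and after device removal. Removal visits are therefore covered. Neighbouring items show how a label and an NA option would look: "For removal visit, was anesthesia required during removal (circle one): Yes No NA (not removal visit". Without them, it is unclear whether the item applies to unscheduled visits. That is an ambiguity, not a separate conflict.
3. **Whether anything lifts it.** The form's general instruction is "For evaluations not performed record ND (not done", with NA for items that do not apply. These codes govern what is written in a field. They do not release staff from an instruction to stop. No other section of the protocol does so either.
4. **Comparison with the timing rules.** Day 7 removal, removal on request on day 5 or 6, and prompt off-site removal are all stated without a photographer condition. At the clinic the conflict is slight: the photographer is a member of the clinic staff, and a short wait on day 7 is still removal on day 7. Off site, waiting for a photographer could mean rebooking a removal that is already late.
5. **Comparison with the purpose of the photographs.** The day 7 list under Data Collection names photographs taken after removal. Under Male Circumcision Using ShangRing Device, the day 7 photograph comes before the wound is cleaned and dressed. Checking for a photographer before starting is therefore sensible. Stopping when none is found is not needed for either purpose.
6. **Consequence of delay.** Under Procedure for Handling Clients Lost-to-Follow-Up, the protocol cites a study with no severe or serious adverse events among men who wore the ring beyond seven days. It adds that leaving the device on may be safe but "this is not the recommended standard of care for the purposes of this evaluation".
7. **Frequency.** The protocol gives no expected number of off-site removals, of visits without a photographer, or of refusals, so none is estimated here.

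**The case against.** The strongest reply has four parts.

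- **Refusal does not trigger the stop.** If a client declines while a photographer is in the room, the answer is Yes and nothing on the form holds removal. A reader might infer that clients who decline photographs are denied or delayed removal. The documents do not support that. The sentence on the photo frame can be read as a rule on how photographs are taken, and the right to refuse stands in the Photography section and on the screening form. This part stands. What remains is that the follow-up form does not repeat that right.
- **The item has a practical reason.** Because the photograph precedes cleaning and dressing, a photographer found missing midway could leave an undressed wound waiting. This also stands and supports keeping the check, though not the stop.
- **The delay at the clinic is trivial.** This is accepted. It does not cover off-site removal. Nothing says that an off-site team would lack a person to take photographs, but nothing ensures one either, and the form gives no alternative.
- **Staff would apply the protocol body over the form.** They may. The item contains no pointer to the body, however, and an instruction that is safe only when ignored should be corrected.

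**Conclusion.** The point holds in a limited form. The form states an instruction that, if followed, holds device removal for an optional evaluation photograph, and no other text lifts it. The exposure is mainly off-site removal of overdue devices, in a number the documents do not give. Harm is probably limited, given the protocol's own account of delayed removal. No endpoint, analysis set, sample size or estimate is affected.

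A reader might go further and call this a material safety hazard. The cited evidence on prolonged wear and the availability of clinic staff as photographers do not support that. The conclusion assumes that staff follow the form as printed and that an off-site visit may sometimes lack a photographer. It is a minor, cheap improvement.

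**What to change.** Change the item in Appendix XII as follows.

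- Label it as applying to the removal visit.
- Keep the check for a photographer before starting, but replace the stop with a recorded response: photo taken, client declined, photographer not available, or NA.
- State on the form that removal and wound care are not to be delayed for photographs.
- Apply the frame, client ID, date and pain-score rule only to photographs that are taken.

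The cost is a one-line edit to one form and a few removal visits without photographs. That slightly reduces the material for verifying adverse events and documenting healing. The recorded response would also show how often photographs were missing and why.
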